#### **Safety Analysis**

Safety outcomes will be assessed by adverse event reporting in active and placebo treated study subjects.

Overall safety and tolerability will be assessed by evaluating the incidence of treatment emergent adverse events (TEAE), vital signs, and other safety variables. Treatment-emergent AEs will be defined as any AEs, regardless of relationship to study drug, which occurs on or after the first double blind dose date and up to 30 days after the last dose date of the double-blind study drug.

Treatment-emergent adverse events (treatment at time of event) will be summarized using the Medical Dictionary for Regulatory Agencies (MedDRA) coding dictionary.

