## **9.2 Procedures**

### **9.2.1 Collection and Reporting of AEs**

#### ***9.2.1.1 PTE and AE Collection Period***

Collection of PTEs will commence from the time the subject signs the informed consent to participate in the study and continue until the subject is first administered study immunotherapy (visit 2) or until screen failure. For subjects who discontinue prior to study immunotherapy administration, PTEs are collected until the subject discontinues study participation.

Collection of AEs will commence from the time that the subject is first administered study immunotherapy (visit 2). Routine collection of AEs will continue until visit 14 .

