#### ***9.2.1.2 PTE and AE Reporting***

At each study visit, the investigator will assess whether any subjective AEs have occurred. A neutral question, such as “How have you been feeling since your last visit?” may be asked. Subjects may report AEs occurring at any other time during the study. Subjects experiencing a serious PTE must be monitored until the symptoms subside and any clinically relevant changes in laboratory values have returned to baseline or there is a satisfactory explanation for the change. Non-serious PTEs, related or unrelated to the study, need not to be followed-up for the purposes of the protocol.

All subjects experiencing AEs, whether considered associated with the use of the study immunotherapy or not, must be monitored until the symptoms subside and any clinically relevant changes in laboratory values have returned to baseline or until there is a satisfactory explanation

for the changes observed. All PTEs and AEs will be documented in the PTE/AE page of the CRF, whether or not the investigator concludes that the event is related to the immunotherapy. The following information will be documented for each event:

1. Event term.
2. Start and stop date.
3. Severity.
4. Investigator's opinion of the causal relationship between the event and administration of study immunotherapy (related or not related) (not completed for PTEs).
5. Investigator's opinion of the causal relationship to the study immunotherapy, including the details of the suspected immunotherapy administration.
6. Action concerning study immunotherapy (not applicable for PTEs).
7. Outcome of event.
8. Seriousness.

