#### 9.2.2 Collection and Reporting of SAEs

When an SAE occurs through the AE collection period it should be reported according to the following procedure:

A sponsor SAE form must be completed, in English, and signed by the investigator immediately or within 24 hours of first onset or notification of the event. The information should be completed as fully as possible but contain, at a minimum:

An SAE should be reported to the sponsor (described in the separate contact information list) within 1 business day of first onset or subject's notification of the event. The principal investigator should submit the completed SAE form within 10 calendar days. The information should be completed as fully as possible but contain, at a minimum:

- A short description of the event and the reason why the event is categorized as serious.
- Subject identification number.
- Investigator's name.
- Name of the study immunotherapy.
- Causality assessment.

The SAE form should be transmitted within 24 hours to the attention of the contact listed in Section 1.0.

Any SAE spontaneously reported to the investigator following the AE collection period should be reported to the sponsor if considered related to study participation.

Reporting of Serious PTEs will follow the procedure described for SAEs.

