#### **12.1.4 Safety Analysis**

Overall safety and tolerability will be assessed by evaluating the incidence of TEAE, laboratory tests, vital signs, and other safety variables. Treatment-emergent adverse events will be defined as any AEs, regardless of relationship to study immunotherapy, that occur on or after the first double blind immunotherapy administration date and up to 30 days after the last dose date of the double-blind immunotherapy and will be assigned to the treatment at the time of the event.

Treatment-emergent adverse events will be summarized using the full analysis set. Adverse events will be summarized using the MedDRA coding dictionary. In general, AEs will be tabulated at each of the following levels: overall summary (subject with at least 1 AE), the MedDRA system organ class (SOC) and the MedDRA preferred term (PT). Tabulations at each level of a term will present count (n) and percentage of subjects reporting any event for that term. Subjects reporting more than one occurrence for the term (level) being summarized will be counted only once and assigned to the drug assignment at time of the event.

Laboratory test variables will be summarized by active PMA or placebo assignment and study visit using descriptive statistics. Laboratory data collected from baseline and up to 7 days after a subject's last dose of study immunotherapy will be included in the analysis. Markedly abnormal laboratory values will be determined and listed by study group. The number and percentage of subjects with marked abnormality in each of the laboratory parameters will be presented.

Descriptive statistics will be used to summarize vital signs by treatment group and study visit. Vital sign data collected from baseline and up to a subject's last dose of study immunotherapy will be included in the analysis.

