## **Appendix A Schedule of Study Procedures**

Study Week:	Screen (Week 1)	Washout (Week 1-2)	Treatment (Week 3-11)	Follow-up safety assessment (Week 14)
Visit Number:	1	N/A	2-17	18
Discussion and Recruitment	X			
Informed consent	X			
Inclusion/exclusion criteria	X			
Demographics and medical history	X			
Medication history	X			
Physical examination	X			
Vital signs	X		X	
Weight and height	X			
Concomitant medications	X	X	X	X
Concurrent medical conditions	X			X
Skin Testing	X			
Blood Draw	X			X
Post-immunotherapy safety f/u				X
Administer immunotherapy/safety f/u			X	
Clinical Survey (RQLQ) and TNSS	X		X	X
Site return compliance	X		X	X
PTE assessment	X	X		
AE assessment		X	X	X

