## **Appendix H Immunotherapy Injection Schedule**

Visit Day	Vial Number	Dilution	A, B, C (ml)	Injection Volume (ml)
2	#5	1:625	0.05	0.15
3	#5	1:625	0.10	0.30
4	#5	1:625	0.15	0.45
5	#5	1:625	0.20	0.60
6	#4	1:125	0.05	0.15
7	#4	1:125	0.10	0.30
8	#4	1:125	0.15	0.45
9	#4	1:125	0.20	0.60
10	#3	1:25	0.05	0.15
11	#3	1:25	0.10	0.30
12	#3	1:25	0.15	0.45
13	#3	1:25	0.20	0.60
14	#2	1:5	0.05	0.15
15	#2	1:5	0.10	0.30
16	#2	1:5	0.15	0.45
17	#2	1:5	0.20	0.60

---

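### Section 9.2.1.1 ends routine AE collection at visit 14, which conflicts with dosing to visit 17, the 30-day TEAE window and Appendix A, and also shortens the SAE procedure in 9.2.2

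*Combined protocol and SAP*

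**What the plan says.** Section 9.2.1.1 starts AE collection at the first injection (visit 2) and then sets the end: "Routine collection of AEs will continue until visit 14".

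Section 9.2.2 takes its scope from that period. Its procedure opens with "When an SAE occurs through the AE collection period it should be reported according to the following procedure". For later events it is narrower: "Any SAE spontaneously reported to the investigator following the AE collection period should be reported to the sponsor if considered related to study participation".

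The other sections run longer:

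- Appendix H schedules 16 injections at visits 2 to 17. Visit 14 is the first from vial #2, and visits 15, 16 and 17 are the remaining three.
- Sections 8.3.4 and 8.3.5 put a safety assessment at visit 18, after the last injection.
- The Study Summary (Safety Analysis) defines treatment-emergent AEs as those occurring "up to 30 days after the last dose date of the double-blind study drug". Section 12.1.4 gives the same limit: "up to 30 days after the last dose date of the double-blind immunotherapy".
- Section 9.2.1.2 has no cut-off: "At each study visit, the investigator will assess whether any subjective AEs have occurred".
- Appendix A marks AE assessment for visits 2 to 17 and again for visit 18.

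The SAP lists the comparison of AE rates between groups as a secondary outcome.

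**The concern.** The section whose job is to define the collection period stops four visits before the study ends. Dosing escalates, and 6.4 ties dose reduction and withdrawal to injection reactions, so tolerability data matter most at the top doses. Taken at its word, 9.2.1.1 does not require routine collection there or in the month afterwards, although the treatment-emergent AE tables and the SAP's AE comparison assume that those data exist.

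The SAE text inherits the problem. After the collection period, 9.2.2 covers an SAE only if it is reported spontaneously and also judged related. Under a literal reading, an SAE after the maximum dose that is judged unrelated, or that nobody volunteers, falls outside that procedure. Section 10.0 provides for no study committee, so oversight depends on what the site collects and reports.

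**Working it through.** **1. Reproduce the plan's own dose figure.** Section 7.1.4 takes 0.9 ml of 20,000 PNU/ml stock in 100 ml: 0.9 × 20,000 / 100 = 180 PNU/ml in vial #1. The top injection is 0.2 ml per mix of vial #2: 180 / 5 × 0.2 = 7.2 PNU, and 7.2 / 2000 = 0.36%. Both match the section.

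**2. Dose around the stop.** Upper bound per allergen = 180 × (ml per mix) / (dilution factor), from Appendix H:

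| Visit | Vial | ml per mix | PNU |
|---|---|---|---|
| 13 | #3 (1:25) | 0.20 | 1.44 |
| 14 | #2 (1:5) | 0.05 | 1.8 |
| 15 | #2 | 0.10 | 3.6 |
| 16 | #2 | 0.15 | 5.4 |
| 17 | #2 | 0.20 | 7.2 |

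Visits 15 to 17 are the three largest doses, at 2, 3 and 4 times the visit 14 dose.

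**3. Share of cumulative dose, nominal dilutions.** Each vial gives 0.05 + 0.10 + 0.15 + 0.20 = 0.50 ml per mix. In ml of vial #1 equivalent:

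- Total: 0.5/625 + 0.5/125 + 0.5/25 + 0.5/5 = 0.1248
- Visits 15 to 17: (0.10 + 0.15 + 0.20)/5 = 0.0900
- Share: 0.0900 / 0.1248 = 72.1%

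The strength of vial #1 cancels, so the share needs no PNU assumption.

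**4. Same share with the preparation volumes in 7.1.1.** The factors are 105/20 = 5.25 for vial #2, 89/4 = 22.25 for vial #3, 5.25 × 22.25 = 116.8 for vial #4, and 22.25 × 22.25 = 495 for vial #5.

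- Total: 0.5/495 + 0.5/116.8 + 0.5/22.25 + 0.5/5.25 = 0.1230
- Visits 15 to 17: 0.45/5.25 = 0.0857
- Share: 0.0857 / 0.1230 = 69.7%

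If collection is taken to stop before the visit 14 injection, visits 14 to 17 carry 80.1% (nominal) or 77.4% (preparation volumes).

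**5. Where the number may come from.** Section 5.1 still describes a six-week treatment phase. Twice-weekly dosing for six weeks is 12 injections; starting at visit 2 they occupy visits 2 to 13, which makes visit 14 the follow-up. Section 8.3.3 also keeps a shorter count, with visits 1 to 12. Alternatively, Appendix A and 8.1.9 label the final visit as week 14, and that visit is number 18. Both readings point to the final follow-up visit.

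**The case against.** The strongest reply is that this is a stale number, not a decision, and that other current text already requires the collection. Appendix A and 9.2.1.2 call for AE assessment at every visit, and 9.2.1.2 wants all AEs on the case report form. Section 7.1.4 requires observation after each injection, 6.4 makes the next dose depend on the reaction to the last one, and the Appendix J form has space for reactions. Sections 8.3.4 and 8.3.5 add the visit 18 safety assessment. For SAEs, Appendix B item 12 asks for notification within 24 hours with no end date, and the SUSAR reporting in 9.3.1 has none either.

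Most of this stands, and it rules out several stronger inferences that a reader might draw:

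- *That sites would in fact stop at visit 14.* The documents do not show this. A site working from Appendix A would carry on.
- *That about 70% of adverse events would be lost.* The figure is a share of scheduled dose, not an estimate of missed events. It also assumes no step-downs under 6.4.
- *That the AE comparison is biased between arms.* Both arms share the same stop, and nothing shows an imbalance.
- *That the week 14 label leaves follow-up short of 30 days.* No document says on which day of week 14 the visit falls, and 8.3.5 sets it at 30 days after the last injection.

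What the reply does not do is settle the conflict. No rule says which section prevails, and 9.2.2 points to the AE collection period, not to Appendix A. The sections that disagree with 9.2.1.1 show that it is wrong; they do not correct it.

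**Conclusion.** The point holds as an internal inconsistency in an operative safety section. As written, 9.2.1.1 ends routine collection before three of the 16 injections, which carry 69.7 to 72.1% of the scheduled cumulative dose, and before follow-up. It disagrees with the 30-day window in two places, with Appendix A, with 9.2.1.2 and with 8.3.4 and 8.3.5, and it narrows 9.2.2.

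The dose share rests on the full Appendix H schedule and on either the nominal dilutions or the preparation volumes in 7.1.1. The practical loss is probably limited, because the other sections would keep a site collecting, but the documents do not allow it to be quantified. The correction should be made because the section governs safety data and SAE reporting and the change is cheap. It does not touch the primary efficacy analysis.

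**What to change.** In 9.2.1.1, replace the visit 14 limit with: AEs and SAEs are collected through visit 18 and for at least 30 days after the last dose received, including in subjects who stop early; telephone contact is enough if the Early Termination Visit or visit 18 falls before day 30.

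The provision for early stoppers is needed because 8.3.4 lets an Early Termination Visit replace visit 18, and that visit can fall inside the 30-day window. The abstract in 1.2 already accepts follow-up by telephone. Section 9.2.2 needs no edit, since it takes its scope from the collection period. No change to the visit timing or to the diary weeks is needed for this point.

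The cost is one sentence, plus one telephone contact for any subject whose last visit falls before day 30.

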#### ***9.2.1.2 PTE and AE Reporting***

At each study visit, the investigator will assess whether any subjective AEs have occurred. A neutral question, such as “How have you been feeling since your last visit?” may be asked. Subjects may report AEs occurring at any other time during the study. Subjects experiencing a serious PTE must be monitored until the symptoms subside and any clinically relevant changes in laboratory values have returned to baseline or there is a satisfactory explanation for the change. Non-serious PTEs, related or unrelated to the study, need not to be followed-up for the purposes of the protocol.

All subjects experiencing AEs, whether considered associated with the use of the study immunotherapy or not, must be monitored until the symptoms subside and any clinically relevant changes in laboratory values have returned to baseline or until there is a satisfactory explanation

for the changes observed. All PTEs and AEs will be documented in the PTE/AE page of the CRF, whether or not the investigator concludes that the event is related to the immunotherapy. The following information will be documented for each event:

1. Event term.
2. Start and stop date.
3. Severity.
4. Investigator's opinion of the causal relationship between the event and administration of study immunotherapy (related or not related) (not completed for PTEs).
5. Investigator's opinion of the causal relationship to the study immunotherapy, including the details of the suspected immunotherapy administration.
6. Action concerning study immunotherapy (not applicable for PTEs).
7. Outcome of event.
8. Seriousness.

#### 9.2.2 Collection and Reporting of SAEs

When an SAE occurs through the AE collection period it should be reported according to the following procedure:

A sponsor SAE form must be completed, in English, and signed by the investigator immediately or within 24 hours of first onset or notification of the event. The information should be completed as fully as possible but contain, at a minimum:

An SAE should be reported to the sponsor (described in the separate contact information list) within 1 business day of first onset or subject's notification of the event. The principal investigator should submit the completed SAE form within 10 calendar days. The information should be completed as fully as possible but contain, at a minimum:

- A short description of the event and the reason why the event is categorized as serious.
- Subject identification number.
- Investigator's name.
- Name of the study immunotherapy.
- Causality assessment.

The SAE form should be transmitted within 24 hours to the attention of the contact listed in Section 1.0.

Any SAE spontaneously reported to the investigator following the AE collection period should be reported to the sponsor if considered related to study participation.

Reporting of Serious PTEs will follow the procedure described for SAEs.

### **9.3 Follow-up of SAEs**

If information not available at the time of the first report becomes available at a later date, the investigator should complete a follow-up SAE form or provide other written documentation and fax it immediately within 24 hours of receipt. Copies of any relevant data from the hospital notes (eg, ECGs, laboratory tests, discharge summary, postmortem results) should be sent to the addressee, if requested.

All SAEs should be followed up until resolution or permanent outcome of the event. The timelines and procedure for follow-up reports are the same as those for the initial report.

#### **9.3.1 Safety Reporting to the Johns Hopkins IRB and Regulatory Authorities**

The study site investigators, in conjunction with the sponsor, will be responsible for reporting all suspected unexpected serious adverse reactions (SUSARs) and any other applicable SAEs to the Hopkins IRB. Relative to the first awareness of the event by/or further provision to the sponsor or sponsor's designee, SUSARs will be submitted to the regulatory authorities as expedited report within 3 business days for fatal and life-threatening events and 10 business days for other serious events, unless otherwise required by Hopkins IRB regulations.

## **10.0 STUDY-SPECIFIC COMMITTEES**

No study specific committees are being used for this study.

## **11.0 DATA HANDLING AND RECORDKEEPING**

The full details of procedures for data handling will be documented in the Data Management Plan. AEs, PTEs, medical history, and concurrent conditions will be coded using the Medical Dictionary for Regulatory Activities (MedDRA).

### **11.1 CRFs (Paper)**

Completed CRFs are required for each subject who signs an informed consent.

The sponsor will supply the investigative site with paper CRFs. These forms are used to transmit the information collected in the performance of this study to the sponsor and regulatory authorities. All paper CRFs must be filled out legibly in black or blue ballpoint ink.

After completion of the entry process, queries may be issued by the sponsor or contracted CRO and will be answered by the site.

Corrections to the CRF are to be made by making a single-line strikeout of the incorrect information and writing in the revisions. All corrections must be initialed and dated.

The principal investigator must review the CRFs for completeness and accuracy and must sign and date the appropriate CRFs as indicated. Furthermore, the investigator must retain full responsibility for the accuracy and authenticity of all data entered on the CRFs.

After submission of the CRFs to the sponsor, any change of, modification of or addition to the data on CRFs should be made by the investigator with use of change and modification records of CRFs (Data Clarification Form) provided by the sponsor. The principal investigator must review the Data Clarification Form for completeness and accuracy, and must sign and date the form.

After the lock of the clinical study database, any change of, modification of or addition to the data on the CRFs should be made by the investigator with use of a Data Clarification Form provided by the sponsor. The principal investigator must review the data change for completeness and accuracy, and must sign and date.

CRFs will be reviewed for completeness and acceptability at the study site during periodic visits by the study monitor. The sponsor or its designee will be permitted to review the subject's medical and hospital records pertinent to the study to ensure accuracy of the CRFs. The completed CRFs are the sole property of the sponsor and should not be made available in any form to third parties, except for authorized representatives of appropriate governmental health or regulatory authorities, without written permission of the sponsor.

### **11.2 Record Retention**

The investigator agrees to keep the records stipulated in Section 11.1 (clarify correct number) and those documents that include (but are not limited to) the study-specific documents, the identification log of all participating subjects, medical records, source worksheets, all original

signed and dated informed consent forms, copies of all paper CRFs and query responses and detailed records of the study immunotherapy solutions to enable evaluations or audits from regulatory authorities, the sponsor or its designees. The ICH E6 Section 4.9.5 states that the study records should be retained until an amount of time specified by applicable regulatory requirements or for a time specified in the Clinical Study Site Agreement. The investigator should contact and receive written approval from the sponsor before disposing of any such documents.

## **12.0 STATISTICAL METHODS**

### **12.1 Statistical and Analytical Plans**

A statistical analysis plan (SAP) will be prepared and finalized prior to unblinding of subject's treatment assignment. This document will provide further details regarding the definition of analysis variables and analysis methodology to address all study objectives.

A blind data review will be conducted prior to unblinding of subject's treatment assignment. This review will assess the accuracy and completeness of the study database, subject evaluability, and appropriateness of the planned statistical methods.

#### **12.1.1 Analysis Sets**

All efficacy and safety analyses will be analyzed using the full analysis set (FAS). The FAS will consist of all subjects who were randomized and received at least one dose of double-blind study immunotherapy. Efficacy analyses will be analyzed according to the treatment received and safety analyses will be analyzed according to the actual treatment received.

Unless otherwise specified, all statistical tests and confidence intervals will be two-sided and conducted at the 0.05 significance level.

#### **12.1.2 Analysis of Demographics and Other Baseline Characteristics**

Demographic and baseline characteristics (eg, age, race, gender, height, weight, etc) will be summarized using descriptive statistics for all subjects and by Sequence group if necessary. For categorical variables (eg, race, gender, etc) the number and percent of subjects in specified categories will be presented. Unless otherwise specified, descriptive statistics on continuous variables (eg, age, height, weight) will consist of the number of subjects (N), mean, standard deviation (SD), median, minimum and maximum.

